#### 6.4.3. Derivation of Health Outcome Endpoints

##### AIM-D Related Endpoints Derivation

As described in Protocol Amendment 1 Section 6.3, the AIM-D was developed as a daily eDiary with a recall period 24 hours. By design, it is collected in the today diary only. The scoring of the following endpoints is completed in 2 steps.

- Monthly Performance of Daily Activities domain score of the AIM-D
- Monthly Physical Impairment domain score of the AIM -D
- Monthly AIM -D total score

##### Step 1: Calculate AIM-D daily domain score and total score

Daily Performance of Daily Activities score will be calculated based on the summation of items 1-5 and 10 and 11, ranging from 0-35. A daily Performance of Daily Activities domain score will be calculated if 4 or more item scores have non-missing responses. When the response category "I did not have <errands, leisure or social, strenuous activities> planned" (items 2, 4, and 5), is selected, the response will be considered missing. The corresponding Performance of Daily Activities domain score will be calculated by summing the non-missing item scores and dividing by the number of non-missing items and then multiplying by 7, provided that 4 or more item scores are available; otherwise it will be set to missing. The raw daily score will be transformed to a 0-100 scale by multiplying by 100 and dividing by the highest raw score (35).

Daily Physical Impairment scores will be calculated based on the summation of items 6-9, ranging from 0-20. A daily Physical Impairment score will be calculated if 2 or more item scores have non-missing responses. The corresponding Physical Impairment score will be calculated by summing the non-missing item scores and dividing by the number of non-missing items and then multiplying by 4, provided that 2 or more item scores are available; otherwise it will be set to missing. The raw daily score will be transformed to a 0-100 scale by multiplying by 100 and dividing by the highest raw score (20).

A daily total score will be calculated based on the summation of items 1-11, ranging from 0-55. A Total Score will be calculated if 6 or more items scores have non-missing responses. When the response category "I did not have <errands, leisure or social, strenuous activities> planned" (items 2, 4, and 5), is selected, the response will be considered missing. The corresponding Total Score will be calculated by summing the non-missing item scores and dividing by the number of

non-missing items and then multiplying by 11, provided that 6 or more item scores are available; otherwise it will be set to missing. The raw score will be transformed to a 0-100 scale by multiplying by 100 and dividing by the highest raw score (55).

#### Step 2: Calculate Monthly Scores and Baseline Score

Monthly scores will be calculated using the average daily scores only if there are at least 14 non-missing daily scores in the corresponding monthly (28-day) period. The corresponding monthly scores will be calculated by summing the non-missing daily domain scores and dividing by the number of non-missing daily scores, provided that 14 or more daily scores are available; otherwise it will be set to missing.

Monthly activity level score will be calculated by summing the non-missing daily scores and dividing by the number of these scores, provided that 14 or more daily scores are available in the corresponding monthly (28-day) period; otherwise it will be set to missing. Same rule will be applied to the calculation of monthly activity limitation score.

#### MSQ Related Endpoints Derivation

MSQ v2.1 consists of 14 items with a 4-week recall period. The scoring of the MSQ is completed in following 3 steps.

##### Step 1: Final item value assignment.

Precoded item values and final item values for each MSQ item response are shown in [Table 6-10](#).

**Table 6-10      Item Values for MSQ Item Responses**

Response Categories	Precoded Item Value	Final Item Value
None of the time	1	6
A little bit of the time	2	5
Some of the time	3	4
A good bit of the time	4	3
Most of the time	5	2
All of the time	6	1

##### Step 2: Computation of raw domain(dimension) scores

Once a final item value has been assigned to each item, a raw score can be computed for each MSQ domain. Role Function-Restrictive domain includes Items 1 - 7, Role Function-Preventive domain includes Items 8 - 11, and Emotional Function domain includes Items 12 - 14. The raw score for each domain is the algebraic sum of the final item values for all items in that domain.

Missing data handling: if a respondent answered at least half of the items in a domain (or half plus one in the case of scales with an odd number of items), a missing item value can be estimated using the average of the other completed items within the same dimension.

In detail, for MSQ v2.1 Role Function-Restrictive domain, the 7 individual item responses using final item value will be summed, resulting in the raw domain score ranging from 7 to 42 with higher scores indicating better quality of life. If there are missing item responses, the raw domain score will be calculated by summing the non-missing item responses using final item value and

dividing by the number of non-missing items and then multiplying by 7 provided that 4 or more items in the domain are completed; otherwise it will be set to missing. For MSQ v2.1 Role Function-Preventive and Emotional Function domains, the raw domain scores will be calculated similarly using final item value respectively. If there are missing item responses, the corresponding raw domain score will be calculated by summing the non-missing item responses using final item value and dividing by the number of non-missing items and then multiplying by the number of questions in that domain provided that 2 or more domain items are completed; otherwise it will be set to missing.

Step 3: Linear transformation to a 0 to 100 scale.

The transformation formula for each MSQ v2.1 domain are listed below

- Role Function-Restrictive:  $\frac{(\text{raw score}-7)*100}{35}$
- Role Function-Preventive:  $\frac{(\text{raw score}-4)*100}{20}$
- Emotional Function:  $\frac{(\text{raw score}-3)*100}{15}$

#### **6.4.4. Repeated or Unscheduled Assessments of Safety Parameters**

Baseline is defined as the last assessment made before the first dose of double-blind study treatment in the lead-in study. If end-of-study assessments are repeated or if unscheduled visits occur, the last nonmissing postbaseline assessment will be used as the end-of-study assessment for generating summary statistics. However, all postbaseline assessments will be used for PCS value determinations, and all assessments will be presented in the data listings.

#### **6.4.5. Missing Date of the Last Dose of Study Intervention**

When the date of the last dose of the open-label study intervention is missing, all efforts should be made to obtain the date from the Investigator. If it is still missing after all efforts have been made, the last available study intervention date will be used in the calculation of treatment duration.

#### **6.4.6. Missing Severity Assessment for Adverse Events**

If severity is missing for an AE that started before the date of the first dose of open-label study treatment, an intensity of mild will be assigned. If severity is missing for an AE that started on or after the date of the first dose of open-label study treatment, an intensity of severe will be assigned. The imputed values for severity assessment will be used for the incidence summary; the values will be shown as missing in the data listings.

#### **6.4.7. Missing Causal Relationship to Study treatment for Adverse Events**

If the causal relationship to the open-label study treatment is missing for an AE that started on or after the date of the first dose of open-label study treatment, a causality of yes will be assigned. The imputed values for causal relationship to open-label treatment will be used for the incidence summary; the values will be shown as missing in the data listings.

#### 6.4.8. Missing Date Imputation

The following imputation rules only apply to cases in which the start date for AEs is incomplete (ie, partly missing).

##### Missing month and day

If the year of the incomplete start date is the same as the year of the first dose of open-label study treatment, the month and day of the first dose of open-label study treatment will be assigned to the missing fields

If the year of the incomplete start date is before the year of the first dose of open-label study treatment, December 31 will be assigned to the missing fields

If the year of the incomplete start date is after the year of the first dose of open-label study treatment, January 1 will be assigned to the missing fields

##### Missing month only

If only the month is missing, the day will be treated as missing and both the month and the day will be replaced according to the above procedure

##### Missing day only

If the month and year of the incomplete start date are the same as the month and year of the first dose of open-label study treatment, the day of the first dose of open-label study treatment will be assigned to the missing day

If either the year of the incomplete start date is before the year of the date of the first dose of open-label study treatment or if both years are the same but the month of the incomplete start date is before the month of the date of the first dose of open-label study treatment, the last day of the month will be assigned to the missing day

If either the year of the incomplete start date is after the year of the date of the first dose of open-label study treatment or if both years are the same but the month of the incomplete start date is after the month of the date of the first dose of open-label study treatment, the first day of the month will be assigned to the missing day

If the stop date is complete and the imputed start date as above is after the stop date, the start date will be imputed by the stop date.

If the start date is completely missing and the stop date is complete, the following algorithm will be used to impute the start date:

- If the stop date is after the date of the first dose of open-label study treatment, the date of the first dose of open-label study treatment will be assigned to the missing start date

If the stop date is before the date of the first dose of open-label study treatment, the stop date will be assigned to the missing start date

#### 6.4.9. Missing Date Information for Prior or Concomitant Medications

For prior or concomitant medications, including rescue medications, incomplete (ie, partly missing) start dates and/or stop dates will be imputed. When the start date and the stop date are both incomplete for a participant, the start date will be imputed first.

##### 6.4.9.1. Incomplete Start Date

The following rules will be applied to impute the missing numeric fields for an incomplete prior or concomitant medication start date. If the stop date is complete (or imputed) and the imputed start date is after the stop date, the start date will be imputed using the stop date.

###### Missing month and day

If the year of the incomplete start date is the same as the year of the first dose of open-label study treatment, the month and day of the first dose of open-label study treatment will be assigned to the missing fields

If the year of the incomplete start date is before the year of the first dose of open-label study treatment, *December 31* will be assigned to the missing fields

If the year of the incomplete start date is after the year of the first dose of open-label study treatment, *January 1* will be assigned to the missing fields

###### Missing month only

If only the month is missing, the day will be treated as missing and both the month and the day will be replaced according to the above procedure

###### Missing day only

If the month and year of the incomplete start date are the same as the month and year of the first dose of open-label study treatment, the day of the first dose of open-label study treatment will be assigned to the missing day

If either the year of the incomplete start date is before the year of the date of the first dose of open-label study treatment or if both years are the same but the month of the incomplete start date is before the month of the date of the first dose of open-label study treatment, the last day of the month will be assigned to the missing day.

If either the year of the incomplete start date is after the year of the date of the first dose of open-label study treatment or if both years are the same but the month of the incomplete start date is after the month of the date of the first dose of open-label study treatment, the first day of the month will be assigned to the missing day

##### 6.4.9.2. Incomplete Stop Date

The following rules will be applied to impute the missing numeric fields for an incomplete prior or concomitant medication stop date. If the date of the last dose of study treatment is missing, replace it with the last visit date in the imputations described below. If the imputed stop date is before the start date (imputed or nonimputed start date), the imputed stop date will be equal to the start date.

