#### **6.3.5. Prior/Concomitant medications**

*Prior medication* is defined as any medication taken before the date of the first dose of lead-in study treatment.

*Concomitant medication* for this study is defined as any medication taken on or after the date of the first dose of open-label study treatment.

Participants will be listed by Anatomical Therapeutic Chemical (ATC) 4 class and preferred term (PT) for both prior medications and concomitant medications in the Safety population.

Concomitant medications will be listed for the Safety Population.

If a participant took a specific medication multiple times or took multiple medications within a specific therapeutic class, that participant would be counted only once for the coded drug name or therapeutic class. Any prior and concomitant medications will be included in listings.

The medication data will be coded using the World Health Organization (WHO) Drug Global B3 version March 2019 or higher.

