**Missing day only**

If the month and year of the incomplete stop date are the same as the month and year of the last dose of study treatment, the day of the last dose of study treatment will be assigned to the missing day

If either the year of the incomplete stop date is before the year of the date of the last dose of study treatment or if both years are the same but the month of the incomplete stop date is before the month of the date of the last dose of study treatment, the last day of the month will be assigned to the missing day

If either the year of the incomplete stop date is after the year of the date of the last dose of study treatment or if both years are the same but the month of the incomplete stop date is after the month of the date of the last dose of study treatment, the first day of the month will be assigned to the missing day

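### When a medication's start and stop dates are both partial, SAP 6.4.9 lets an imputed start overwrite an earlier recorded stop month, which can wrongly class the drug as concomitant

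*SAP*

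**What the plan says.** SAP 6.4.9 sets the order of work: "When the start date and the stop date are both incomplete for a participant, the start date will be imputed first".

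SAP 6.4.9.1 then gives a tie-break for the start: "If the stop date is complete (or imputed) and the imputed start date is after the stop date, the start date will be imputed using" that stop date. SAP 6.4.9.2 gives one for the stop: "If the imputed stop date is before the start date (imputed or nonimputed start date), the imputed stop date will be equal to" that of the start.

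Two of the ordinary imputation rules matter here. For a start with no month, in the year of the first open-label dose, "the month and day of the first dose of open-label study treatment will be assigned to the missing fields" (6.4.9.1). For a stop with only the day missing, in the same year as the last dose, where "the month of the incomplete stop date is before the month of the date of the last dose of study treatment, the last day of" that recorded month is used (6.4.9.2).

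SAP 6.3.5 classifies from these dates. A prior medication "is defined as any medication taken before the date of the first dose of lead-in study treatment"; a concomitant one "is defined as any medication taken on or after the date of the first dose of open-label study treatment". A drug taken only between those two dates is neither.

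The adverse-event rule in SAP 6.4.8 lets only a complete stop date pull back an imputed start, so it contains no such loop.

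**The concern.** The two tie-breaks give opposite remedies for the same event, an imputed start later than an imputed stop. Under 6.4.9.1 the start moves back; under 6.4.9.2 the stop moves forward. Because the start is imputed first, there is no imputed stop for 6.4.9.1 to act on, and 6.4.9.2 settles the record.

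That is reasonable when the start date is known. It is not reasonable when the start is only a default placed at the first open-label dose and the stop carries a recorded month. A guess then replaces data.

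The prior/concomitant class is at stake. Protocol 4.5.2 restricts interacting drugs and most preventives from before Visit 1 and through the study. A drug recorded as stopped before open-label dosing could therefore be classed as taken together with atogepant.

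**Working it through.** The documents state no figure on this point, so there is none to reproduce. The rules were coded as written and applied to assumed dates, because the documents give neither calendar dates nor the interval between the first lead-in dose and the first open-label dose.

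**Assumed dates.** First open-label dose 15 Jun 2021; last dose 6 Sep 2021 (day 84: 15 Jun + 83 days); first lead-in dose 23 Mar 2021 (12 weeks before open-label dosing).

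**Case A: start 2021 (month missing), stop Feb 2021.**
1. Start first (6.4.9.1): the year equals the first-dose year, so start = 15 Jun 2021.
2. Stop (6.4.9.2): February precedes the month of the last dose, so stop = 28 Feb 2021.
3. Stop is before start, so 6.4.9.2 sets stop = 15 Jun 2021. The stop moves 31 + 30 + 31 + 15 = 107 days, out of its recorded month.
4. Class under 6.3.5: concomitant, not prior.
5. Under the opposite tie-break, start = stop = 28 Feb 2021: prior, not concomitant.

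**Case B: start Oct 2021, stop 2021 (month missing).** Visit 5 is due about 6 Sep + 28 days = 4 Oct, so an October start is possible.
1. Start = 1 Oct 2021; stop = 6 Sep 2021.
2. 6.4.9.2 sets stop = 1 Oct 2021. The recorded October is kept, which is right.
3. The opposite tie-break would set start = 6 Sep 2021 and overwrite the recorded month.

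So neither existing tie-break is right for every record.

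**All partial pairs.** Each date is either year only or year and month, over 2020 to 2022, and pairs impossible on their recorded parts are dropped.
- Start year before stop year: 3 × 13 × 13 = 507.
- Same year: 3 × (1 + 12 + 12 + 78) = 309.
- Total: 816.

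The imputed start falls after the imputed stop in 30 pairs:

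| Start recorded | Stop recorded | Pairs | Recorded month at risk |
|---|---|---|---|
| 2020 | Jan–Nov 2020 | 11 | stop |
| 2021 | Jan–May 2021 | 5 | stop |
| Oct–Dec 2021 | 2021 | 3 | start |
| Feb–Dec 2022 | 2022 | 11 | start |

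6.4.9.2 overwrites the recorded stop month in 11 + 5 = 16 pairs. In the other 3 + 11 = 14 it preserves the recorded start month.

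**Class changes, 6.4.9.2 against the opposite tie-break.** The five pairs with start 2021 and stop Jan–May 2021 all become concomitant. The lead-in interval changes only the class they should have had:

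| Assumed interval | Prior to concomitant | Neither to concomitant |
|---|---|---|
| 8 weeks | 3 | 2 |
| 12 weeks | 2 | 3 |
| 16 weeks | 1 | 4 |
| 24 weeks | 0 | 5 |

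The 11 pairs in 2020 stay prior at 8, 12 and 16 weeks. At 24 weeks (first lead-in dose 29 Dec 2020), 6.4.9.2 moves them to 31 Dec 2020, so they go from prior to neither.

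With a 12-week interval and the first open-label dose on the 15th of each month in turn, the number moving into the concomitant class is 0 in January and rises by one a month to 11 in December. Of these, prior-to-concomitant moves number 0 for January to April, then 1 in May rising to 8 in December.

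The counts show where the rule fails. They are not frequencies, because the pairs are not weighted by how often they occur.

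**The case against.** A reader might infer that the SAP leaves the result to whichever sentence a programmer chooses. The documents do not support that. The start-first sentence makes the outcome determinate: 6.4.9.2 governs, and the reference to an imputed stop in 6.4.9.1 is inert. What remains is a clause without effect and a wrong result for some records.

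A reader might also infer that the cure is to restrict 6.4.9.2 to recorded start dates and let 6.4.9.1 govern otherwise. That corrects Case A but breaks Case B, and in 14 of the 30 conflicts it would overwrite a recorded start month. It would also require 6.4.9.1 to be run again after the stop is imputed.

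It can be argued that placing an uncertain drug on treatment is conservative. That is fair when the recorded parts leave the question open. Here the recorded stop month rules it out.

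The objection on impact largely stands. SAP 3 expects about 3 participants. SAP 6.3.5 lists medications, and the layout of the listings is in a separate document (SAP 1). SAP 5.1 shows partial dates as recorded, so a reader of the listing could see that the stop month precedes dosing. Nothing in the documents shows a summary statistic or an efficacy result that depends on this class, and such a record may never occur.

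**Conclusion.** The point holds in a limited form. With both dates partial, the stated order makes 6.4.9.2 decide, and it can replace a recorded, earlier stop month with an imputed start.

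The move into the concomitant class needs all of the following: a start with no month, in the calendar year of the first open-label dose, and a recorded stop month that ends before that dose. The drug should then be prior, or neither prior nor concomitant, depending on when lead-in dosing began.

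Under the assumed dates this is 5 of 816 possible pairs, of which 2 are prior-to-concomitant at a 12-week interval. The error reaches the assigned class and not the displayed dates. It is a minor defect worth correcting because the rule as written gives a wrong answer and the correction is cheap. All calendar dates and lead-in intervals are assumptions; the conflict between the sections does not depend on them.

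**What to change.** For records with both dates partial, replace the two tie-breaks in SAP 6.4.9.1 and 6.4.9.2 with one rule, applied after each date has been imputed:

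- If the imputed start is later than the imputed stop and the start month is missing, set the start equal to the imputed stop.
- If the imputed start is later than the imputed stop and the stop month is missing, set the stop equal to the imputed start.
- No imputed date may override a recorded month or year.

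In each of the 30 conflicting pairs exactly one date has a recorded month, so the rule resolves all of them: start to stop in 16, stop to start in 14. The order of imputation then no longer matters. Where one of the two dates is complete, the present rules can stay, since the complete date is never the one moved.

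The cost is one short paragraph in the SAP and a few lines in the medication-date program. No change to data collection is needed.

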**Missing month and day**

If the year of the incomplete stop date is the same as the year of the last dose of study treatment, the month and day of the last dose of study treatment will be assigned to the missing fields

If the year of the incomplete stop date is before the year of the last dose of study treatment, December 31 will be assigned to the missing fields

If the year of the incomplete stop date is after the year of the last dose of study treatment, January 1 will be assigned to the missing fields

